4.1.1.1. Study Periods

The study will be divided into the following periods for each subject.

4.1.1.2. Screening Period/Inclusion

Following subject signature of the informed consent form (ICF) (the signing of the ICF indicates the start of the study), subject eligibility will be confirmed during a Screening period that will occur within 28 days prior to the first dose of investigational medicinal product (IMP) for subjects in the Safety Lead-in phase and Expansion phase. Subjects will be enrolled based on local IDH1 mutation results. All subjects will have a radiographic evaluation (computed tomography [CT] or magnetic resonance imaging [MRI]) at Screening to confirm the presence of measurable disease (at least one measurable lesion, as defined by RECIST v1.1) according to the site radiologist/Investigator. Additional screening procedures for all subjects include medical, surgical, and medication history; complete physical examination, height, and weight; vital signs; Eastern Cooperative Oncology Group (ECOG) performance status; 12-lead ECG; evaluation of left ventricular ejection fraction (LVEF) (echocardiogram [ECHO], multiple gated acquisition [MUGA] scan, or by other method according to institutional practice); and clinical laboratory assessments (hematology, chemistry, thyroid function tests, coagulation, and pregnancy test). A buccal swab for germ-line mutation analysis will also be obtained at Screening.

In case of non-inclusion of a subject, it is the Investigator's responsibility to ensure, in accordance with the local standards of care and medical practices, that:

- The reason of non-inclusion is explained to the subject.
- Any event associated with any procedure/condition required by the study protocol (e.g., an event occurring following the discontinuation of a forbidden treatment) is collected.
- Adequate alternative medical care is proposed to the subject.

A non-inclusion visit is not mandatorily carried out, provided these requirements are met and documented in the medical file of the subject.

4.1.1.3. Treatment Period

The study will include 2 separate phases, the Safety Lead-in phase and the Expansion phase. Eligible subjects can participate in one of the 2 phases only. Subjects enrolled in Safety Lead-in phase will not participate in the Expansion phase.

Safety Lead-In Phase

Following the Screening period, the first 6 subjects enrolled will receive a dose of 500 mg QD of ivosidenib in combination with nivolumab [] mg/kg and ipilimumab [] mg/kg CCI [] followed by nivolumab CCI [] mg CCI [] (up to 24 total doses of nivolumab). Based on the DLT evaluation of 500 mg QD, an additional 6 subjects could be enrolled to test an alternative dose of 250 mg QD. DLTs will be evaluated through Cycle 2 (i.e., during the first 42 days, 21 days/cycle). Subjects may receive up to a maximum of 24 months of nivolumab. Subjects who are still deriving clinical benefit after 24 months may continue to receive ivosidenib monotherapy until disease progression, unacceptable toxicity, or other discontinuation criteria are met (see Section 4.3).

Starting from Cycle 5, subjects in the Safety Lead-in phase who discontinue one IMP for a reason other than disease progression may continue to receive the other IMP with Sponsor

approval until disease progression or other discontinuation criteria (including the criterion of having received a maximum of 24 months of nivolumab) are met.

Expansion Phase

Following the Screening period, subjects enrolled into the Expansion phase will receive ivosidenib at the RCD as determined by the Safety Lead-in phase in combination with nivolumab [] mg/kg and ipilimumab [] mg/kg [] followed by nivolumab at [] mg [] mg [] Subjects may receive up to a maximum of 24 months of nivolumab. Subjects who are still deriving clinical benefit after 24 months may continue to receive ivosidenib monotherapy until disease progression, unacceptable toxicity, or other discontinuation criteria are met (see Section 4.3).

Starting from Cycle 5, subjects in the Expansion phase who discontinue one IMP for a reason other than disease progression may continue to receive the other IMP with Sponsor approval until disease progression or other discontinuation criteria (including the criterion of having received up to a maximum of 24 months of nivolumab) are met.

All subjects will undergo safety assessments throughout the Safety Lead-in and Expansion phase treatment periods, which will include limited physical examination, vital signs including weight, ECOG performance status, ECG, and clinical laboratory assessments (hematology, chemistry, thyroid function tests, coagulation, and pregnancy testing). Serial blood samples will be drawn at specified time points from all subjects receiving ivosidenib in combination with nivolumab and ipilimumab to determine ivosidenib plasma concentration–time profiles and PK parameters, PD, nivolumab and ipilimumab serum concentrations, and anti-drug antibody (ADA) parameters. Archival tumor (collected on Cycle 1 Day 1 [C1D1] only), and buccal swab samples (collected at Screening) and blood samples will be collected for exploratory biomarker analysis. All subjects will undergo radiographic evaluations (MRI or CT) to assess the extent of their disease at Screening and at regular intervals while on-treatment and/or at any time when progression of disease is suspected.

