The study will consist of 2 phases:

Safety Lead-in Phase

The Safety Lead-in phase will evaluate the safety and tolerability of ivosidenib in combination with nivolumab and ipilimumab in order to determine the RCD. This phase will enroll approximately 6-12 DLT-evaluable subjects with nonresectable or metastatic CCA with an IDH1 mutation.

The first 6 subjects enrolled will receive a dose of 500 mg once daily (QD) of ivosidenib in combination with nivolumab 3 mg/kg IV infusion and ipilimumab 1 mg/kg IV infusion concurrently once every 3 weeks (Q3W) for 4 doses followed by nivolumab at 480 mg IV once every 4 weeks (Q4W) until progression or unacceptable toxicity (up to a maximum of 24 months of nivolumab). DLTs will be evaluated through Cycle 2 (*i.e.*, during the first 42 days, 21 days/cycle). Based on the DLT evaluation of 500 mg QD, an additional 6 subjects may be enrolled to test an alternative dose of 250 mg QD. DLT evaluability is determined by subjects who have received the combination therapy and experienced a DLT through Cycle 2 or who have received at least 2 doses of nivolumab and ipilimumab, respectively, and at least 75% of ivosidenib at the assigned dose through Cycle 2 without experiencing a DLT through Cycle 2. There will be no intra-subject dose escalations or reductions of nivolumab or ipilimumab allowed. Subjects must be dosed with nivolumab and/or ipilimumab no fewer than 19 days from the previous dose for the first 4 cycles and no fewer than 25 days from the last dose in Cycle 5 and beyond. A minimum of 6 DLT-evaluable subjects will be required to evaluate the safety and tolerability of the combination. Subjects who are not DLT evaluable will be replaced. A data review team (DRT) composed of Sponsor medical, safety, and statistical representatives, together with Principal Investigator(s), will review the available safety data when at least 6 DLT-evaluable subjects have completed at least 2 cycles of treatment or experienced a DLT within the first 2 cycles.

Dose Stopping Criteria and De-escalation

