In both phases, subjects will receive ivosidenib at the assigned dose on Days 1 through 21 in 21-day cycles for first 4 cycles followed by 28-day cycles starting with Cycle 5. Dosing is continuous, there are no planned rest periods. On days when subjects are receiving nivolumab and ipilimumab, ivosidenib should be administered approximately 30 minutes before the start of the infusion. It is recommended that each dose should be taken with or without food. Subjects taking ivosidenib with food should be advised to avoid grapefruit or grapefruit products and avoid consuming a high-fat meal (Please refer to examples of low-fat and high-fat meals in [Appendix 11](#)).

No premedication is required prior to subjects receiving the first dose of ivosidenib.

Nivolumab

Nivolumab will be administered as an approximately 30-minute infusion at 3 mg/kg IV Q3W for the first 4 doses followed by 480 mg Q4W until progression and for up to a maximum of 24 months. Nivolumab infusion is to be administered prior to ipilimumab.

Infusion duration: Nivolumab is to be infused over an approximately 30-minute (-5/+10 minutes) period. Subjects should be monitored for infusion reactions for 30 to 60 minutes after completing the nivolumab infusion. If a subject has an infusion reaction, a follow-up call approximately 24 hours after completion of infusion is recommended to ensure that the event is resolved. Premedications are not recommended for the first dose of nivolumab.

Ipilimumab

Ipilimumab will be administered as an approximately 30-minute infusion at 1 mg/kg IV Q3W for 4 total doses.

Infusion duration: Ipilimumab is to be infused within 30 minutes after the end of nivolumab infusion over an approximately 30-minute (-5/+10 minutes) period. The time in between nivolumab and ipilimumab infusions is expected to be within approximately 30-minutes.

Subjects should be monitored for infusion reactions for 30 to 60 minutes after completing the ipilimumab infusion. If a subject has an infusion reaction, a follow-up call approximately 24 hours after completion of infusion is recommended to ensure that the event is resolved.

Duration of Treatment:

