6.2. IMP Dispensing

After completion of IRT, IMPs will be allocated, dispensed, and tracked via RTSM by the pharmacist/responsible individual of the healthcare establishment upon prescription of the Investigator only. The Investigator may only use the IMPs provided for the subjects involved in the study and treated under the Investigator's responsibility. All dosages of nivolumab and ipilimumab are prescribed to the subject and all dose changes during the study must be done via RTSM and recorded in the eCRF. For doses of ivosidenib, should a subject be unable to receive or return to the site for dose administration, delivery of the dose to the subject's home is permitted.

One drug kit of ivosidenib will be dispensed to the subject at Day 1 of each cycle. Nivolumab will be infused to the subject at Day 1 of each cycle. The number of vials of nivolumab allocated and the volume to infuse will be calculated in RTSM based on subject weight (from Cycle 1 to Cycle 4) and will be the same (48 mL) beginning at Cycle 5. At Day 1 of the first 4 cycles (Cycle 1 to Cycle 4), ipilimumab will be infused to the subject. The number of vials of ipilimumab allocated and the volume to infuse will be calculated based on subject weight.

The pharmacist/responsible individual of the healthcare establishment prepares the treatment in accordance with the Pharmacy Manual and documents it in the drug kit tracking file or equivalent validated tracking system. The individual then either sticks the drug kit label to the paper label collection form or assigns a drug kit number in the validated electronic tool based on site procedures, or scans the QR code in the validated electronic tool at the site level to log the dispensation.

The drug kit will be identified by a 6-digit number for identification, tracking, and stock management purposes.

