7.4. Continuation of Treatment Beyond Radiographic Progression

In the event of radiographic progression per RECIST v1.1 but in the absence of clinical deterioration, worsening ECOG performance status, or disease progression that may compromise organ function, the subject may continue to receive study treatment with ivosidenib, nivolumab, and/or ipilimumab at the discretion of the treating physician in consultation with the Sponsor. Nivolumab will be permitted for up to a maximum of 24 months from date of first dose. If there is clinical deterioration or continued radiographic progression documented on subsequent imaging, treatment with either ivosidenib, nivolumab, or both will be discontinued, and the subject will complete the EOT and Safety Follow-up visits and enter Survival Follow-up.

All other elements of the main consent including description of reasonably foreseeable risks or discomforts, or other alternative treatment options, will still apply. Treatment beyond progression may be administered during or after localized interventions (surgery/radiation therapy).

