1.2. Study design

This is a Phase 1/2, non-comparative, multicenter, open-label study of ivosidenib, an oral mutant IDH1 inhibitor, administered in combination with nivolumab and ipilimumab. Participants are required to have a histologically confirmed diagnosis of cholangiocarcinoma (CCA), a local molecular IDH1 gene-mutation CCA and not eligible for curative resection, transplantation, or ablative therapies. The study is conducted in adult participants with nonresectable or metastatic CCA. Participants must have progression of disease or treatment intolerance and have received at least 1 but not more than 2 prior treatment regimens for advanced disease (nonresectable or metastatic). All participants must have received either a gemcitabine- or a 5-fluorouracil (5-FU)-based chemotherapy regimen.

This study consists of a Safety Lead-in phase followed by an Expansion phase as shown in [Figure \(1.2\) 1](#) and [Figure \(1.2\) 2](#), respectively.

The Safety Lead-in phase will enroll up to approximately 6-12 DLT-evaluable participants. The first 6 participants enrolled will receive a dose of 500 mg once daily (QD) of ivosidenib in combination with nivolumab 3 mg/kg and ipilimumab 1 mg/kg concurrently once every 3 weeks (Q3W) for 4 doses followed by nivolumab 480 mg once every 4 weeks (Q4W) until progression (up to a maximum of 24 months of nivolumab). DLTs will be evaluated through Cycle 2 (i.e., during the first 42 days, 21 days/cycle). Based on the DLT evaluation of 500 mg QD by the Data Review Team (DRT), an additional 6 participants may be enrolled to test an alternative dose of 250 mg QD in order to reach the RCD after further review of the DRT before the Expansion phase.

The Expansion phase is conducted in 2 IDH1-mutated CCA subpopulations:

- Cohort 1: anti-PD-L1-naïve subpopulation: This subpopulation includes up to approximately 40 participants with nonresectable or metastatic CCA who have not received any anti-PD-L1 therapy.
- Cohort 2: anti-PD-L1 previously treated subpopulation: This subpopulation includes up to approximately 40 participants with nonresectable or metastatic CCA who have received anti-PD-L1 therapy.

Participants enrolled in this phase receive the RCD of ivosidenib in combination with nivolumab 3 mg/kg and ipilimumab 1 mg/kg concurrently Q3W for 4 doses followed by nivolumab at 480 mg every 4 weeks until progression (up to a maximum of 24 total months of nivolumab).

Figure (1.2) 1 - Safety Lead-in Phase

[figure not shown]

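### For the Safety Lead-in, Section 4.1.1.3 sets two non-equivalent ceilings on nivolumab, 24 total doses and 24 months, and does not say which governs

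*Protocol*

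**What the plan says.** Protocol Section 4.1.1.3, under the Safety Lead-in phase, describes the regimen and closes that sentence with "up to 24 total doses of nivolumab". Later in the same paragraph it says: "Subjects may receive up to a maximum of 24 months of nivolumab". Both statements are current text and legible. The doses and schedule beside the first are blacked out there, but the synopsis gives them: "once every 3 weeks (Q3W) for 4 doses followed by nivolumab at 480 mg IV once every 4 weeks (Q4W").

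All other statements of the limit are in months. They are in the synopsis, Sections 4.1.1, 4.1.3.3, 4.1.4, 4.1.5, 4.3.1, 5.4.1 and 7.4, the Expansion part of 4.1.1.3, and SAP Section 1.2, which has "until progression (up to a maximum of 24 months of nivolumab"). Section 7.4 fixes the start of the clock: "Nivolumab will be permitted for up to a maximum of 24 months from date of first dose".

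Two rules hang on the limit. Section 4.1.1.3 lets a participant who still benefits after 24 months go on with ivosidenib alone. Section 5.4.1 lists completion of 24 months of nivolumab as a reason for stopping. Neither mentions a number of doses.

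**The concern.** A dose count and a calendar period are the same limit only if the schedule makes them so. With three-week spacing at first and four-week spacing later, 24 doses take less than 24 months. A site that applies the dose count and a site that applies the calendar would stop nivolumab at different times in identical participants.

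At stake is when a participant who is still benefiting stops nivolumab and moves to ivosidenib alone. A participant held to 24 doses would reach that point before the 24 months named in the switch rule, and Section 5.4.1 has no reason specific to a dose count. The paragraph concerns the Safety Lead-in, which SAP Section 5 says is the only phase that ran.

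**Working it through.** **Inputs**
- Dose limit: 24 (protocol 4.1.1.3, Safety Lead-in).
- Time limit: 24 months (same paragraph), counted from the first dose (7.4).
- Schedule: four doses every 3 weeks, then every 4 weeks (synopsis).
- Cycle lengths: "21-day cycles for first 4 cycles followed by 28-day cycles starting with Cycle 5" (synopsis).
- Doses per cycle: "Nivolumab will be infused to the subject at Day 1 of each cycle" (6.2), so one.
- Days per month: 30.4375 (SAP 5.2.1), so 24 months = 24 × 30.4375 = 730.5 days.

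**Dose dates, in days after the first dose**
- Doses 1 to 4: 0, 21, 42, 63.
- Dose n from the fifth on: 84 + 28 × (n − 5).

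**Dose limit expressed as time**
- Dose 24: 84 + 28 × 19 = 616 days = Week 88.
- 616 / 30.4375 = 20.2 months.
- Gap to the time limit: 24 − 20.2 = 3.8 months. If the 28 days after dose 24 are counted as treated time, (616 + 28) / 30.4375 = 21.2 months and the gap is about 2.8 months.

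**Time limit expressed as doses**
- Doses 25 to 28 fall at 644, 672, 700 and 728 days; dose 29 would fall at 756.
- Doses before Week 104 (728 days): 27. Doses within 730.5 days: 28.
- Excess over the dose limit: 27 − 24 = 3, or 28 − 24 = 4.

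**Sensitivity**

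| Variant | Dose 24 at | Doses within 730.5 days |
|---|---|---|
| Nominal schedule | 616 days (20.2 months) | 28 |
| First 4-weekly dose 28 days after dose 4 | 623 days (20.5 months) | 27 |
| Shortest permitted intervals, 19 then 25 days | 551 to 557 days (18.1 to 18.3 months) | 30 to 31 |
| Every interval 2 days long, 23 then 30 days | 662 days (21.7 months) | 26 |

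The shortest intervals come from the synopsis ("no fewer than 19 days from the previous dose for the first 4 cycles", and 25 days from Cycle 5). No variant gives 24 doses in a full 24 months. If a month is read as 28 days (672 days in all), 25 or 26 doses fit on the nominal schedule or with the 28-day gap after dose 4. The count comes down to 24 only if that reading is combined with every interval running 2 days long.

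**Another reading of the 24**

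If 24 counts only the flat 4-weekly doses, the last falls at 12 + 4 × 23 = Week 104, or 728 days. The total is then 4 + 24 = 28 doses, the same number that fits in 24 months.

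**The case against.** A reader might infer that the two limits cannot both hold. They can. Both are ceilings, and a participant who has had 24 doses by Week 88 satisfies each. On schedule the dose ceiling binds first. With enough delay, about 730.5 − 616 = 114 days in total before dose 24, the time ceiling would bind first. Section 8.12.2 contemplates long delays. This objection stands, and what remains is ambiguity: nothing says that the earlier limit governs, while the switch rule and the discontinuation reason refer to time alone.

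The flat-dose reading is the strongest defence. The parenthesis directly follows the flat-dose leg of the regimen, some text next to it is blacked out, and on this reading the figures agree exactly. Against it, the phrase refers to total doses of nivolumab, and the four weight-based doses are nivolumab too. The reading is possible, but the text does not establish it.

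A further defence is that the dose count appears once and the months appear everywhere else. That shows where the inconsistency lies. It does not settle which limit was intended for the Safety Lead-in.

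A reader might also infer that the 100-day window for immune-mediated events, or planned exposure, becomes undefined. The documents do not support this. SAP Sections 4.2 and 5.4.1.2 count the window from the actual last nivolumab dose. SAP Section 5.2.1 builds planned dose and dose intensity from planned doses and cycles, not from either maximum.

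Finally, practical reach is small. SAP Section 5 reports 7 participants, and SAP Section 1 dates the termination letter 21 August 2024. Assume that dosing began no earlier than 1 June 2023, the start of the target month in the synopsis; actual dates are not given. Then at most 447 days, or 447 / 30.4375 = 14.7 months, had passed by the letter, short of dose 24 on the nominal schedule. This stands, with one reservation. Section 4.3.1 lets participants who benefit stay on treatment, with nivolumab up to 24 months, if termination was not for safety. The SAP does not state the reason.

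**Conclusion.** The point holds as an internal inconsistency in a stopping threshold. Section 4.1.1.3 gives two ceilings that are not equivalent and no rule for choosing between them. On the literal reading and the nominal schedule, they differ by 3 to 4 doses and by about 3.8 months measured to the date of dose 24. Delays narrow the difference and shorter permitted intervals widen it. If the 24 was meant for flat doses only, there is no numerical conflict, and the fault is wording that does not say so.

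The supported consequence is an ambiguous point for stopping nivolumab and moving to ivosidenib alone. Practical reach is low: one phrase, one phase, 7 participants, and a terminated study. The documents do not show that any participant reached or approached dose 24, nor whether any remained on nivolumab after termination.

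**What to change.** Reconcile the two statements in the Safety Lead-in paragraph of Section 4.1.1.3 so that one maximum appears, or state how the two interact and which doses the 24 counts. Check the result against the synopsis, Sections 4.1.1, 4.1.4, 4.1.5, 4.3.1, 5.4.1 and 7.4, and SAP Section 1.2, so that the switch to ivosidenib alone and the discontinuation reason follow the same limit. This review takes no position on which limit is right.

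The cost is one phrase. Since the study has been terminated, a short clarification to sites for any participant still on nivolumab may serve in place of an amendment. No analysis in the SAP needs to change.

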4.1.1.4. End of Treatment/Withdrawal Visit

All subjects will undergo an End of Treatment (EOT) assessment within 7 days after the last dose of IMP (for combination, this is to occur after all 3 IMPs have been discontinued). However, when this is not possible (e.g., dose delay more than 7 days), EOT assessment can be performed at the 30-day safety follow-up visit. Every effort must be made to perform protocol-specified evaluations unless consent to participate in the study is withdrawn.

4.1.1.5. Post-Withdrawal Follow-up and End of Study

Safety Follow-up: Following discontinuation of study treatment, a post-treatment Safety Follow-up visit is to occur 30 (+5) days after the last dose of ivosidenib and immunotherapy. Subjects will be followed for an additional 100 (+5) days after the last dose of immunotherapy, unless they have started another anti-cancer therapy, whichever occurs earlier. Every effort must be made to perform protocol-specified evaluations unless consent to participate in the study is withdrawn.

PFS and Overall Survival Follow-up: Subjects who discontinue study treatment for reasons other than disease progression or withdrawal of consent from treatment and are alive by EOT will enter PFS follow-up with the same schedule of assessments as before study treatment discontinuation, until documented disease progression, death, the start of subsequent anti-cancer therapy, withdrawal of consent, or the end of study/study termination. Following discontinuation of study treatment, all subjects will be followed for survival. Subjects will be contacted every 12 weeks (\pm 2 weeks) after the subject experiences documented disease progression or begins subsequent anti-cancer therapy. This contact will continue for up to 2 years after the last subject has been enrolled, or until end of study, withdrawn consent, or are lost to follow-up, or the Sponsor has terminated the study, whichever occurs first.

Each subject will have an End of Study visit defined as the time at which the subject has permanently discontinued treatment and has completed the Safety Follow-up visit and survival follow-up period, or has died, been lost to follow-up, or withdrawn consent from the study or the Sponsor has terminated the study, whichever occurs first.

